A secondary objective is to assess the risk of new-onset AF identified within 8 days after *Arexvy* vaccination.

Study Design

Self-controlled risk interval (SCRI) design.

Population

Health plan members \geq 50 years of age will be eligible if they: 1) received one dose of *Arexvy*; 2) had 365 days of continuous medical and pharmacy enrolment prior to *Arexvy* receipt; 3) had continuous enrolment through the end of the follow-up period; 4) had no evidence of a second dose of *Arexvy* during the follow-up period; and 5) had no evidence of another medical product indicated for RSV disease prevention prior to receipt of *Arexvy* or during the follow-up period.

Variables

Arexvy receipt; new-onset GBS; new-onset ADEM; new-onset AF.

Data sources

Five Research Partners (RPs) (Carelon, CVS Health, HealthPartners, Humana, Point32Health) participating in the United States (US) FDA's Sentinel System.

Study size

Using a background rate for GBS of 4.5 cases per 100 000 person-years, a total of 69 GBS cases in the combined risk and control intervals will provide 80% power to reject the null hypothesis of no association when the true relative risk (RR) is \geq 2.0. Approximately 4.4 million vaccinated patients are expected to be needed to accrue the number of cases of GBS. Using a background rate for ADEM of 0.45 cases per 100 000 person-years, a total of 12 cases in the combined risk and control intervals provides 80% power to reject the null hypothesis of no association when the true RR is \geq 7.0. Approximately 3.9 million vaccinated patients are expected to be needed to accrue the number of cases of ADEM.

Data analysis

SCRI-based analyses will use conditional Poisson regression to determine incidence rate ratios (IRRs) of outcomes with 95% confidence intervals (CIs).

Milestones

Data collection will begin **CC** (the month when vaccinations began) and continue through 30 June 2030 or until the number of cases needed to power the study with adequate precision have been accrued, whichever is earlier. An inferential analysis of each outcome will be conducted when the required number of cases have accrued. A final report will be submitted to the US FDA by 31 December 2031.

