7.5. Study size

The sample size and power calculations are estimated for the primary outcomes of the study, GBS and ADEM, and the primary risk (days 1-42) and control (days 43-84) windows. In the US, background rates of GBS reported in the literature range from 1.6 to 6.3 per 100 000 person-years in the overall population. In those ≥ 60 years of age, the IRs vary from 2.4 to 4.7 per 100 000 person-years in studies conducted over several years between 1935 and 1987 [Law, 2021]. More recent publications are reporting IR ≥ 4 GBS cases per 100.000 person-years in older adults. A study conducted in the US on background rates of adverse events of special interest reported a GBS IR of 4.6 per 100.000 person-years in adults ≥ 65 years of age [Moll, 2023]. The background rate in the analysis conducted by [Lloyd, 2024] was 4.4 per 100,000 person-years (unpublished). Background rates of ADEM range from 0.3 to 0.6 per 100 000 person-years in the overall population [Pohl, 2016].

The estimated number of vaccinated individuals needed to detect an association between *Arexvy* and the outcomes, assuming 80% statistical power, a two-sided alpha = 0.05, and an equal duration of 42 days for the risk window and 42 days for the control window, are

reported in Table 8 for GBS and ADEM for a range of RRs to be detected and a range of IR for the outcomes. Table 9 is for AF and is based on risk and control windows of 8 days.

Using a background rate for GBS of 4.5 cases per 100 000 person-years (taken as the average from [Lloyd, 2024] (4.4) and Moll, 2023 (4.6)), a total number of 69 cases in the combined risk and control intervals provides 80% power to reject the null hypothesis of no association when the true RR is \geq 2.0. Approximately 4.4 million vaccinated patients are needed to accrue the number of cases of GBS (Table 8).

Using a background rate for ADEM cases of 0.45 per 100 000 person-years, a total number of 12 cases in the combined risk and control intervals provides 80% power to reject the null hypothesis of no association when the true RR is \geq 7.0. Approximately 3.9 million vaccinated patients are needed to accrue the number of cases of ADEM (Table 8).

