In the US, an IR of 16.6 cases per 1000 person-years has been reported for AF in 2018 for those 55 years and older, with a range of 6.9 to 52.5 cases per 1000 person-years for those aged 55-64 and \geq 85 years of age, respectively [Williams, 2020]. For this secondary outcome, to detect a RR of \geq 2, 69 cases will be needed (Table 9).

Table 8Estimated number of cases and vaccinated health plan members
needed to detect an association between RSV vaccination and GBS
or ADEM using a SCRI design, with 80% power, a two-sided alpha =
0.05, under different scenarios for relative risk and background
incidence rate: 42-day risk and control window

Relativ e risk	Total number of cases (control and risk periods) *	Numbe r of cases in control period	0.3 per 100 000 PY	0.45 per 100 000 PY	0.6 per 100 000 PY	2 per 100 000 PY	3 per 100 000 PY	4 per 100 000 PY	4.5 per 100 000 PY	5 per 100 000 PY	6 per 100 000 PY
1.25	634	282	81746428 6	54497619 1	40873214 3	12261964 3	8174642 9	6130982 2	5449762 0	4904785 8	4087321 5
1.50	194	78	22610714 3	15073809 6	11305357 2	33916072	2261071 5	1695803 6	1507381 0	1356642 9	1130535 8
2.00	69	23	66672620	44448413	33336310	10000893	6667262	5000447	4444842	4000358	3333631
2.50	41	12	34785715	23190477	17392858	5217858	3478572	2608929	2319048	2087143	1739286
3.00	29	8	23190477	15460318	11595239	3478572	2319048	1739286	1546032	1391429	1159524
4.00	20	4	11595239	7730159	5797620	1739286	1159524	869643	773016	695715	579762
5.00	15	3	8696429	5797620	4348215	1304465	869643	652233	579762	521786	434822
6.00	13	2	5797620	3865080	2898810	869643	579762	434822	386508	347858	289881
7.00	12	2	5797620	3865080	2898810	869643	579762	434822	386508	347858	289881

*Total number of cases was calculated using the method described by Musonda et al. [Musonda, 2006], assuming that the length of the risk period is the same as the length of the control period.

Table 9Estimated number of cases and vaccinated health plan members
needed to detect an association between RSV vaccination and AF
using a SCRI design, with 80% power, a two-sided alpha = 0.05,
under different scenarios for relative risk and background incidence
rate (8-day risk and control windows)

Relative risk	Total number of cases (control and risk periods)*	Number of cases in control period	1 per 1000 PY	2 per 1000 PY	5 per 1000 PY	10 per 1000 PY	50 per 1000 PY
1.25	634	282	12875063	6437532	2575013	1287507	257502
1.50	194	78	3561188	1780594	712238	356119	71224

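### The 3.9 million vaccinees given for ADEM correspond to 16 expected cases at RR 7, not 12, because Table 8 rounds 1.5 control-window cases up to 2

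*Protocol*

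**What the plan says.** Section 7.5 sizes the primary outcomes "assuming 80% statistical power, a two-sided alpha = 0.05"; the risk and control windows both last 42 days. For ADEM it fixes the rate ("Using a background rate for ADEM cases of 0.45 per 100 000 person-years") and the case target ("a total number of 12 cases in the combined risk and control intervals provides 80% power"), with a true RR of at least 7, and then converts cases to people: "Approximately 3.9 million vaccinated patients are needed to accrue the number of cases of ADEM (Table 8". The Synopsis says the same: "Approximately 3.9 million vaccinated patients are expected to be needed to accrue the number of cases of ADEM".

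The source is the last row of Table 8, which begins "7.00 12 2 5797620 3865080 2898810". These entries are the RR, the total cases, the control-window cases, and the vaccinees at 0.3, 0.45 and 0.6 per 100,000 person-years. The table's footnote gives the method for the total number of cases only. Nothing in the protocol states or justifies rounding the control-window count to a whole number.

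Four other provisions bear on the point:
- Section 7.3.2.1 expects about 30% of requested charts to be unobtainable.
- Section 7.7.2.1 excludes events without charts from the primary analysis.
- Section 7.7 triggers each final analysis by the number of events accrued.
- Section 7.9.1 ends data collection in June 2030 or when the needed cases have accrued.

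**The concern.** The ADEM row disagrees with itself. Twelve total cases with 2 in the control window leave 10 in the risk window, a ratio of 5, yet the row is labelled RR 7. The RR 6 row (13 cases) and the RR 7 row (12 cases) also print the same number of vaccinees in every rate column, although under one expected-count formula the two targets need different populations.

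At stake is the feasibility statement for a primary objective. Section 7.9 names low uptake as the threat to sample size, so a reader judging whether ADEM can be answered by June 2030 will compare projected uptake with 3.9 million. The figure stands beside 4.4 million for GBS as if both had the same basis, but the GBS figure carries no rounding and the ADEM figure carries one third. Any later adjustment scaled from 3.9 million, for chart loss or a different background rate, would inherit the excess. A reader could also mistake the excess for a planned allowance.

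**Working it through.** **Inputs, all from Section 7.5 and Table 8.** Two-sided alpha 0.05, power 80%, risk and control windows of 42 days each, ADEM rate 0.45 per 100,000 person-years, RR 7, 12 total cases. One assumption: a year of 365.25 days, which the protocol does not state. It reproduces all nine entries of the 0.45 column to the unit, whereas 365 days would give 3,862,434 for RR 7.

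**Step 1, case target.** The Musonda signed-root likelihood-ratio formula with equal windows gives 11.02 cases at RR 7, and the table prints 12. With exactly 12 cases, a two-sided exact binomial test rejects in favour of increased risk at 10 or more risk-window cases and has 82% power at RR 7. The target stands.

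**Step 2, the printed vaccinee number.** With equal windows, expected control cases = total/(1 + RR) = 12/8 = 1.5. Vaccinees = control cases / (rate × 42/365.25).
- With 2 control cases: 2/(0.0000045 × 42/365.25) = 3,865,080, the printed value.
- With 1.5 control cases: 1.5/(0.0000045 × 42/365.25) = 2,898,810.
- Ratio: 2/1.5 = 1.333.

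**Step 3, what 3,865,080 yields.** Two control cases at RR 7 imply 14 risk cases, so 16 in total. It yields 12 only at RR 5 (2 + 10).

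**Step 4, range over the protocol's ADEM rates.** At 0.3 and 0.6 per 100,000 person-years the unrounded numbers are about 4.35 and 2.17 million, against 5.80 and 2.90 million printed.

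**Step 5, all rows.**

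| RR | Total cases | Total/(1+RR) | Printed control cases | Excess in vaccinees |
|---|---|---|---|---|
| 1.25 | 634 | 281.78 | 282 | 0.1% |
| 1.5 | 194 | 77.6 | 78 | 0.5% |
| 2 | 69 | 23 | 23 | 0% |
| 2.5 | 41 | 11.71 | 12 | 2.4% |
| 3 | 29 | 7.25 | 8 | 10.3% |
| 4 | 20 | 4 | 4 | 0% |
| 5 | 15 | 2.5 | 3 | 20% |
| 6 | 13 | 1.857 | 2 | 7.7% |
| 7 | 12 | 1.5 | 2 | 33.3% |

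Table 9 uses the same control counts. At RR 7 and 1 per 1,000 person-years, 2/(0.001 × 8/365.25) gives the printed 91,313. The AF target row (RR 2) is exact, as is GBS: 23/(0.000045 × 42/365.25) = 4,444,842.

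**Step 6, what each ADEM figure delivers at RR 7.** Assumptions: Poisson counts and, for the chart-loss rows, 30% of true cases lost.

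| | 2,898,810 | 3,865,080 |
|---|---|---|
| Expected cases | 12 | 16 |
| Chance of at least 12 | 54% | 87% |
| Expected cases after 30% chart loss | 8.4 | 11.2 |
| Chance of at least 12 after that loss | 14% | 44% |
| Power averaged over Poisson counts, likelihood-ratio test (no chart loss) | 84% | 92% |
| Same, exact binomial test | 70% | 85% |

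Restoring 12 expected cases after 30% loss needs 2,898,810/0.7 = about 4.14 million.

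**The case against.** The strongest reply is that no decision rests on this number. Data collection ends on a date or on accrued cases, each analysis is triggered by events, and Section 7.5 attaches the 80% power to the 12 cases, not to the vaccinees. The error errs on the safe side, and the 2 control cases are printed for anyone to see. All of this stands and limits the weight of the point. It does not make the sentence correct: 3.9 million is not the population expected to yield 12 cases at RR 7.

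A second reply is that a bare 2.9 million would be a worse planning number, with only a 54% chance of reaching 12 cases and no room for missing charts. This also stands, and it shapes the fix.

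Three stronger readings are tempting, and the protocol supports none of them:
- A reader might infer that the excess is a deliberate margin or chart allowance. Nothing says so. A margin of 0% at RR 2 and 33% at RR 7 is what rounding produces, and it falls short of 4.1 million in any case.
- A reader might infer that the error hides ADEM reaching its target before GBS. The printed 3.9 and 4.4 million already show that order. It also depends on the true RRs: at RR 1, 12 ADEM cases need about 11.6 million vaccinees (6/(0.0000045 × 42/365.25)) and 69 GBS cases about 6.7 million (34.5/(0.000045 × 42/365.25)), which reverses it.
- A reader might infer that the study is mis-powered. The case target is sound, and the averaged power at a given population depends strongly on the test used.

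**Conclusion.** The point holds as an arithmetic error in a stated sample size for a primary objective. For its own inputs the ADEM vaccinee number is one third too high: 3,865,080 gives 16 expected cases at RR 7, and 12 correspond to 2,898,810. The same rounding inflates the RR 5 row by 20%, RR 3 by 10% and RR 6 by 8%; the effect is 2.4% or less at RR 1.25, 1.5 and 2.5, and nil at RR 2 and RR 4.

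The consequence is limited. The error is conservative and leaves the case target and the stopping rule as they are. The expected counts rest on the protocol's rate, windows and RR, with 365.25 days per year. The chances of reaching 12 cases also assume Poisson variation, and the chart-loss figures assume that true cases are lost at the protocol's approximate 30%. The result does not make 2.9 million a sufficient target.

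**What to change.** In Tables 8 and 9, show total/(1 + RR) with decimals and use it unrounded in the vaccinee calculation; round up only the final number of vaccinees. In Section 7.5 and the Synopsis, state what the ADEM number represents, in one of two ways:
- about 2.9 million as the bare expectation for 12 confirmed cases at RR 7, always with an explicit allowance for unobtainable charts beside it (about 4.1 million if 30% of cases are lost); or
- 3.9 million retained, with the statement that it yields 16 expected cases at RR 7 before chart loss and about 11 after 30% loss.

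If power is quoted for a number of vaccinees, name the test: at 2.9 and 3.9 million, before chart loss, it is 84% and 92% by likelihood-ratio test, and 70% and 85% by exact binomial test.

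The cost is a recalculation of two tables and an edit to two sentences. The case targets and study conduct do not change.

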Table 7 ICD-10-CM diagnosis codes for new-onset AF case-finding algorithm

Full Description	Code
Paroxysmal atrial fibrillation	148.0
Unspecified atrial fibrillation	148.91

Validation of New-Onset AF events: Materials for medical record review (including the abstraction and adjudication forms with case classifications and SOPs), will be developed prior to having results from the first monitoring query.

Since AF is a common health outcome among older adults, we will evaluate the PPV (95% CI) of our proposed algorithm for new-onset AF within a random sample of vaccinees who meet the algorithm. Our focus is on PPV because a sufficiently high PPV provides confidence that identified outcomes are true events.

As described in Section 7.3.2.1 above, we will identify a random sample of patients with new-onset AF across our RPs according to the algorithm developed in Table 4 and based on the number of charts needed in Table 3. If we obtain a PPV \geq 80%, it will provide reassurance that majority of new-onset AF events ascertained using the algorithm are true cases and reduce concerns regarding outcome misclassification; a claims data-only analysis will be conducted, possibly including adjustment for the PPV. If, contrary to expectation, the PPV of a coding algorithm is found to be below 80%, the inferential analyses will be restricted to chart-confirmed cases only. In this situation, additional charts will be sought to obtain 69 confirmed cases. This is based on an assumption of an IR between 10 and 50 per 1000 person-years and a RR of 2.

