2.00	69	23	1050094	525047	210019	105010	21002
2.50	41	12	547876	273938	109575	54788	10958
3.00	29	8	365251	182626	73050	36525	7305
4.00	20	4	182626	91313	36525	18263	3653
5.00	15	3	136969	68485	27394	13697	2740
6.00	13	2	91313	45657	18263	9132	1827
7.00	12	2	91313	45657	18263	9132	1827

*Total number of cases was calculated using the method described by Musonda et al. [Musonda, 2006], assuming that the length of the risk period is the same as the length of the control period.

PY=person-years

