7.7. Data analysis

Whenever possible, publicly available analytic tools created for the FDA's Sentinel System will be used. These are the same tools used by the FDA. Modifications to the tools may be needed to meet study objectives, in which case Sentinel's SAS programming data quality assurance (QA) SOPs will be followed. All the statistical analyses will be done in SAS 9.4 or higher.

Descriptive monitoring analyses, described in Section 7.7.1 below, will be conducted annually. Inferential analyses will be conducted following the methods in Section 7.7.2 as well as the SAP that will be developed and finalized prior to conducting the analyses.

For each outcome, the final inferential analysis will be performed once the number of events needed has accrued. For GBS and ADEM, depending on the accrual pace, separate analyses will be done (e.g., if GBS events accrue faster than ADEM), otherwise analysis of both primary outcomes will be combined in a single final analysis at study end. For new-onset AF, since these events are relatively more common, the final analysis will be conducted earlier than the GBS and ADEM final analyses (Table 10).

Outcome	Target risk to detect	Analysis sequence
AF	RR ≥2	Phase 1
GBS	RR ≥2	Phase 2
ADEM	RR ≥7	Phase 3

Table 10Sequence of analysis

ADEM: acute disseminated encephalomyelitis; AF: atrial fibrillation; GBS: Guillain-Barré syndrome; RR: relative risk

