7.7.3. Secondary analysis/Exploratory analysis

The analysis of new-onset AF, a secondary outcome, will be conducted using the same analytic approach as the primary outcomes described above in Section 7.7.2.1 in terms of the SCRI design as well as identification of fatal events. However, as explained in detail in Section 7.3.2.4, all claims-identified cases will be included for new-onset AF assuming the PPV for the diagnostic coding algorithm is $\geq 80\%$.

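### The 69-case AF target counts true cases, but it is also the only target for the claims-only analysis, where false positives pull the IRR towards 1 and the correction is optional

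*Protocol*

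**What the plan says.** Protocol 7.5 states that for AF "69 cases will be needed (Table 9") to detect an RR of 2 or more. Table 9 is built "with 80% power, a two-sided alpha = 0.05", for 8-day risk and control windows. Its footnote cites the Musonda method, "assuming that the length of the risk period is the same as the length of the control period". No term for misclassified cases appears.

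Section 7.3.2.4 then splits the AF analysis on the estimated PPV:

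- **PPV below 80%:** only chart-confirmed cases are analysed, and charts are sought until there are 69 confirmed cases. The stated basis is: "This is based on an assumption of an IR between 10 and 50 per 1000 person-years and a RR of 2".
- **PPV at least 80%:** "a claims data-only analysis will be conducted, possibly including adjustment for the PPV". Section 7.7.3 agrees: "all claims-identified cases will be included for new-onset AF assuming the PPV for the diagnostic coding algorithm is" at least 80%. No separate case target is given for this branch.

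On timing, 7.7 says: "For each outcome, the final inferential analysis will be performed once the number of events needed has accrued". Table 10 puts AF first in the sequence, with a target RR of 2 or more. Section 7.9 accepts that some claims outcomes will not be true events and says quantitative bias analyses may be done.

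**The concern.** A count of 69 confirmed cases and a count of 69 claims cases do not carry the same information. If up to one in five claims cases is false, and the false ones are unrelated to vaccination, they add about equally to both windows and move the ratio towards 1. The plan ties 69 to confirmed cases in one branch and leaves it unchanged in the other.

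Two things follow. An analysis run close to 69 claims cases would have less than the 80% power shown in Table 9. More lastingly, the IRR itself is diluted whatever the number of cases. In a safety study that bias runs towards finding no harm, and with many cases it would come with a narrow interval around the wrong value. The only remedies in the text are worded as options.

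**Working it through.** **Inputs from the protocol.** Two-sided alpha 0.05, power 80%, RR 2, 69 cases and equal 8-day windows (7.5, Table 9); PPV threshold 80% (7.3.2.4); background AF rate 16.6 per 1000 person-years (7.5).

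**Assumption, not in the protocol.** False-positive cases have RR 1 and fall equally in the two windows.

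**Step 1: reproduce the 69.** With ρ the RR and r = 0.5 the risk share of observation time, the Musonda signed-root formula is

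- A = 2[(ρr/(ρr+1−r))·ln ρ − ln(ρr+1−r)]
- B = (ln ρ)²/A · ρr(1−r)/(ρr+1−r)²
- n = (1.960 + 0.842·√B)²/A

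At ρ = 2, A = 0.1133 and B = 0.9426, so n = 68.09, rounded up to 69. Power at 69 is 80.5%. The same formula returns every other case total in Table 9 (634, 194, 41, 29, 20, 15, 13, 12). The table is correct for true cases.

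**Step 2: apparent RR at PPV 80%.** Take 1 true control-window case and 2 true risk-window cases. The PPV can be read in two ways.

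- *80% of all counted cases are true (pooled).* Total 3/0.8 = 3.75, so 0.75 are false, 0.375 per window. Apparent RR = 2.375/1.375 = 1.73.
- *80% of control-window cases are true.* Total 1/0.8 = 1.25, so 0.25 are false per window. Apparent RR = 2.25/1.25 = 1.80.

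**Step 3: power at 69 counted cases, and cases needed for 80%.** Power = Φ[(√(nA) − 1.960)/√B], with A and B taken at the apparent RR.

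| PPV and reading | Apparent RR | Power at 69 | Cases for 80% |
|---|---|---|---|
| 100% | 2.00 | 80.5% | 69 |
| 90%, control window | 1.90 | 74.4% | 79 |
| 90%, pooled | 1.86 | 71.4% | 85 |
| 80%, control window | 1.80 | 67.0% | 94 |
| 80%, pooled | 1.73 | 60.8% | 108 |

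Other approximations at PPV 80% agree closely (pooled to control-window reading): normal binomial 60.4-66.7%, arcsine 61.1-67.3%, Wald 59.0-64.8%, likelihood ratio 62.2-68.3%. The exact binomial test is lower throughout (52.4-59.0%), but it gives only 74.1% with no false positives at all.

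**Step 4: what more cases change.** At apparent RR 1.73, power is 97% with 200 counted cases and above 99.9% with 500. The apparent RR stays at 1.73.

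**Step 5: vaccinees.** Background cases per vaccinee in 8 days = 0.0166 × 8/365.25 = 0.0003636.

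- 69 true cases: 23/0.0003636 ≈ 63,000.
- 108 claims cases (pooled): 108 × 0.8/3 = 28.8 true control cases, 28.8/0.0003636 ≈ 79,000.
- 94 claims cases (control window): 94/3.5 = 26.9 true control cases, 26.9/0.0003636 ≈ 74,000.

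**Step 6: the correction recovers the RR.** With N counted cases, subtract (1−PPV)·N/2 from each window (pooled reading). For 69 cases split 43.7 to 25.3 at PPV 80%, subtract 6.9 from each: 36.8/18.4 = 2.0.

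**The case against.** A reader might infer that Table 9 is miscalculated. It is not: 69 reproduces, and the chart-confirmed branch already asks for 69 confirmed cases.

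A reader might also infer that the AF analysis will miss a true doubling more than a third of the time. The documents do not support that, for four reasons.

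- The 61-67% applies only to a claims-only analysis run at about 69 claims cases. The protocol makes 69 a number needed, not a cap. Monitoring queries are cumulative and expected to be annual (7.1), and 7.7.3 includes every claims-identified case.
- The claims-only branch cannot open until the PPV has been estimated. That takes about 63 adjudicated charts, with 30% or more of records expected to be unavailable (7.3.2.1), so about 63/0.7 = 90 claims cases are sampled from one or two partners alone. Table 3 starts at 1,000 identified AF cases.
- The partners listed in 7.4 have about 17.5 million members aged 50 or over (4.4 + 7 + 0.247 + 5.56 + 0.248 million). The 79,000 vaccinees above are about 0.45% of them.
- Even at 69 cases, the control-window reading gives 33.0% missed, which is under a third.

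The dilution may also be smaller than shown. Under 7.7.2.3 the primary PPV counts confirmed cases only, and a clinician's clear AF diagnosis without a monitoring study is classed as possible (7.3.2.4). If half of the unconfirmed 20% were real AF, the effective PPV would be 90%, with apparent RR 1.86 and 71% power at 69 cases.

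All of this stands, and it reduces the power problem to a minor one. It does not remove the dilution, which is the same at any case count. Method details can go to the SAP, but here the protocol itself fixes the target and the trigger and words the correction as discretionary.

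**Conclusion.** The point holds in a limited form. The 69 is correct for true AF cases, and it is the only target the protocol gives for an analysis of claims-identified cases. With null false positives spread evenly over the windows, a PPV of 80% turns a true RR of 2 into about 1.73-1.80. Power would be about 61-67% at about 69 claims cases, and 94-108 would be needed for 80% (79-85 at PPV 90%).

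Because the count will probably be well above 69, the practical loss of power is likely small. What lasts is an IRR biased towards 1 in the claims-only branch with no firm commitment to correct it. PPV 80% is the threshold on the estimate, so a higher PPV, or real AF among the possible cases, shrinks the effect. In the other direction, 63 charts give about ±10 points (1.96 × √(0.8 × 0.2/63) = 0.099), so an estimate of 80% is compatible with a true PPV near 70%. The apparent RR would then be 1.61 on the pooled reading. This is a gap between two branches of the plan and should be closed before the AF analysis.

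**What to change.** - In 7.5, Table 9 and 7.3.2.4, state that 69 means true (confirmed) AF cases, and set the claims-only minimum as a function of the estimated PPV: about 94-108 at PPV 80% and 79-85 at 90%, naming the reading of PPV used.
- In 7.3.2.4, replace the optional wording with a required PPV-corrected IRR, reported beside the crude IRR, with the uncertainty in the estimated PPV carried into its interval.
- State that the claims-only AF analysis uses all events accrued at the time it is run, not the first 69.

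The cost is protocol wording, one extra analysis and a minimum trigger later by roughly 11,000 to 16,000 vaccinees at 16.6 per 1000 person-years (74,000 or 79,000 against 63,000). The corrected IRR will have a somewhat wider interval. No additional chart review is needed.
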